5 PARTICIPANT ENTRY

5.1 CONSENT

Consent will be a two-stage process for patients undergoing PPCI for STEMI. Verbal assent will be brief prior to the PPCI and first blood sample, so as not to lead to a reduction in the quality of patient care (MI outcomes are related to the door to balloon time with PPCI). A

shortened patient information sheet will be read to the patient and if verbal assent is gained it will be recorded in the clinical notes and the site file. This is in line with NRES guidelines that suggest that patients admitted with STEMI are considered as unconscious patients initially.

Following emergency PCI and IMR measurement, when the patient is pain free and has been able to rest, a full patient information sheet will be proffered and written consent sought. If the patient does not want to be part of the trial, he or she will be withdrawn from the study and future tests will not be performed. Treatment will continue in accordance with clinical guidelines. The patients' participation in the trial will last for 3 months. At the end of three months a Cardiac MRI scan will be performed unless there are specific contraindications. Vital status will be determined on discharge and at three months when patients turn up to have their cardiac MRI scan. If a patient fails to attend Cardiac MRI scan appointment in three months' time, a telephone call will be made to the relevant GP to determine the vital status of the patients.

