5.6 WITHDRAWAL CRITERIA

Patients are able to withdraw from the trial if they wish without the need to provide reasons and without their care being affected or compromised. Patients who decide to withdraw their consent to participate in the study will have all samples collected up to the time of withdrawal disposed of in appropriate manner. All information collected on the patient for the purpose of the study will be erased. The withdrawal shall be recorded in the study patient identification log. The treatment of the patient will continue in accordance with clinical guidelines should the participant choose to withdraw or not. If a patient dies after obtaining verbal assent but before gaining a written consent, they will still be included in the study and data collected up to the time of death will still be used. Patients who will need administration of glycoprotein IIb/IIIa inhibitors during or post PPCI procedure and patients who fail to have Cangrelor or Ticagrelor for unexpected circumstances will be withdrawn from the study and their data will not be collected.

Safety stopping criteria:

A participant would be withdrawn from the trial if the Clinician feels that continued participation would be unsafe for the participant.

This could include, but not restricted to:

- An anaphylactic shock
- An SAE occurring

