6.2 Sampling and Dosing

6.2.1 Study subjects will have a $P2Y_{12}$ inhibitor administered (Ticagrelor or Cangrelor) after recorded verbal assent following randomisation. The time of loading dose will be recorded and the patient transferred to the cardiac catheterization suite. After the insertion of the radial or femoral sheath, 10 ml of whole blood will be drawn from this sheath at the first intracoronary balloon inflation time. A further 10 ml will be taken 4 hours post dosing (or as close as is practicable). Further sampling (15 ml) on the ward will take place 24-36 hours post dosing from an anticubital vein using a 21-gauge needle (see study summary tables). Samples taken will be analysed to assess $P2Y_{12}$ activity using VerifyNow TM (Accumetrics, San Diego, California, USA) and VASP Flow Cytometry tests. Peak Troponin levels will be assessed as well using the same blood samples.

6.2.2 Dosing: Patients will be divided into two arms; Oral Ticagrelor (50 patients) and Intravenous Cangrelor (50 patients) arms.

Ticagrelor arm: Patients will receive Ticagrelor 180mg loading dose on the cardiology ward prior to transfer to the catheter lab. Thereafter, a maintenance dose of 90mg twice daily will be given and continued for 12 months duration.

Cangrelor arm: Patients will receive Cangrelor administered at a rate of 30 micrograms/kg intravenous bolus followed immediately by 4 micrograms/kg/min intravenous infusion. The bolus and infusion will be initiated in the cardiac catheter lab prior to the PCI procedure and continued for at least two hours or for the duration of the procedure (to increase up to three hours), whichever is longer. 30 minutes prior to stopping Cangrelor infusion, Ticagrelor 180 mg will be given followed by 90mg twice daily maintenance dose continued for duration of 12 months. Cangrelor will be obtained directly from The Medicines Company, retained at the

pharmacy department at New Cross Hospital and issued by the pharmacy department for our clinical trial purposes only. Ticagrelor will be received by the pharmacy department and designated for our clinical trial purposes only.

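### Section 5.6 lets a clinician who knows the arm withdraw a patient from the whole trial on safety grounds, with an SAE as a listed example, and does not keep that patient in follow-up

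*Combined protocol and SAP*

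**What the plan says.** Under the safety stopping criteria, section 5.6 states: "A participant would be withdrawn from the trial if the Clinician feels that continued participation would be unsafe for the participant". The examples are introduced by "This could include, but not restricted to" and are anaphylactic shock and "An SAE occurring". The section does not say which assessments continue after a safety withdrawal, or what happens to data already collected.

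The assessments at stake are set out in sections 4, 4.1, 5.1 and 6.2.1 and in Appendix 2:

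- an ECG at 90-120 minutes after PPCI
- blood samples at 4 hours and at 24-36 hours, the later one including troponin
- vital status at discharge and at three months
- CMR at three months, planned for all 100 participants.

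On vital status, section 5.1 says: "Vital status will be determined on discharge and at three months when patients turn up to have their cardiac MRI scan". It adds a telephone call to the GP if the patient misses the CMR appointment.

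**The concern.** Leaving a treatment and leaving a trial are different events, and section 5.6 treats them as one. Patients with a serious event are those whose later samples, infarct size and survival are most informative. If they leave follow-up, the data that remain come from patients who did better. The decision is made after randomisation, after an adverse outcome, by a clinician who knows the arm. The loss may therefore differ between arms and depend on outcome, and the analysis cannot repair that without further assumptions. Section 7 does not say how patients withdrawn on safety grounds are analysed.

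The rule also fits the design poorly. Cangrelor is infused for at most three hours (sections 4 and 6.2.2), after which both arms are on ticagrelor. Trial withdrawal after that point removes no cangrelor exposure, but it can remove scheduled observation.

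**Working it through.** **Step 1. What withdrawal means elsewhere in the protocol.**

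| Situation | Section | Stated consequence |
|---|---|---|
| Patient declines written consent | 5.1 | "he or she will be withdrawn from the study and future tests will not be performed" |
| Patient withdraws consent | 5.6 | Samples are disposed of; "All information collected on the patient for the purpose of the study will be erased" |
| Glycoprotein IIb/IIIa inhibitor needed, or study drug not received | 5.6 | Patient "will be withdrawn from the study and their data will not be collected" |
| Death between verbal assent and written consent | 5.6 | Patient stays in; data up to death are used |
| CMR appointment missed | 5.1 | GP is called for vital status |
| Clinician withdraws the patient for safety | 5.6 | Nothing stated |

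In each of the three withdrawal routes with a stated consequence, tests or data are lost. The one retention rule is limited to early death. The GP call is tied to a missed appointment and is not stated to cover withdrawn patients. A site applying section 5.6 after an SAE thus has no text telling it to continue follow-up, and three parallel rules pointing the other way.

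**Step 2. Which outcomes are exposed.** By the end of PPCI the balloon-time sample, IMR and TIMI flow are complete (Appendix 2). A later withdrawal puts at risk only the assessments listed above that are still to come.

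**Step 3. Illustrations.** The plan has no figure to reproduce. Section 7.1 reports no formal sample size calculation, and no SAE rate, SD or dropout rate is given. All rates and effects below are assumptions.

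*Precision.* Inputs: 50 per arm (section 4); assumed loss r in both arms; assumed difference of 0.5 SD; two-sided alpha 0.05. With n = 50 × (1 − r), power ≈ Φ(0.5 × √(n/2) − 1.96).

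| r | CMR scans left | Power |
|---|---|---|
| 0 | 100 | 70.5% |
| 2% | 98 | 69.7% |
| 5% | 95 | 68.3% |
| 10% | 90 | 66.0% |
| 20% | 80 | 60.9% |

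*Vital status.* Assume 2 known deaths among 50 in one arm and k withdrawn patients of unknown status. The three-month death proportion lies between 2/50 = 4% and (2 + k)/50. The upper limit is 6% for k = 1, 10% for k = 3 and 14% for k = 5.

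*Selective loss for infarct size.* The fall in an arm's observed mean equals the proportion removed × the excess infarct size of those removed. Assume 12% removed in one arm and 4% in the other (6 and 2 of 50), with infarcts 10 points larger than in the rest of the arm. The falls are 0.12 × 10 = 1.2 and 0.04 × 10 = 0.4, a spurious difference of 0.8 points. With an assumed SD of 8 to 12 points, the standard error of the difference is SD × √(2/50) = 1.6 to 2.4. The bias is then 0.8/2.4 = 0.3 to 0.8/1.6 = 0.5 standard errors.

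**The case against.** The strongest reply is that section 5.6 only permits withdrawal. A reader might infer that any SAE removes the patient. The text does not support that: the test is the clinician's judgement of safety, and the examples are things it could include. If mainly observation remains after the infusion, a clinician may seldom judge continued participation unsafe. This stands, and it means the rule may be used rarely.

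Second, loss of follow-up after a safety withdrawal is inferred from the other routes. This also stands. The inference is reasonable because the routes agree, but it is an inference. Likewise, nothing says that omitting only the pressure-wire step requires leaving the trial, and section 5.1 already exempts patients with contraindications from CMR.

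Third, a reader might infer that the outcomes of SAEs are hidden from the committee that can terminate the trial under section 8. That goes too far. All SAEs are to be reported, with forms sent within 24 hours (sections 9.2 and 9.2.2), so the triggering event is known. Adverse event recording stops at 36 hours for every patient (section 9.1.1), so much of the later course goes unrecorded with or without withdrawal. Section 9.1.2 also excludes many procedural events from the SAE definition, which narrows this example.

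Fourth, a reader might infer that a death after withdrawal would be missed at both vital-status checks. The documents support only that it could be, because the GP call does not expressly exclude withdrawn patients.

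Finally, this is a pilot not powered for clinical outcomes, and its procedural outcomes are complete by the end of PPCI. That limits the consequence but does not remove it: CMR and the later platelet samples are listed outcome measures.

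**Conclusion.** The point holds in this form: section 5.6 states a rule for withdrawal from the trial on safety grounds, names an SAE as an example, and does not preserve follow-up. Applied in line with the protocol's other withdrawal rules, it could remove already scheduled outcome and vital-status data in a way related to both outcome and arm. It should be corrected.

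The size and direction of any bias cannot be given. The 0.8-point figure is not an estimate. It assumes that every patient with an SAE is withdrawn, would otherwise have been alive and scanned, and has a larger infarct, and that SAE rates differ threefold between arms. Even then the bias is at most half a standard error under the assumed SDs. The precision loss is modest across the range shown. What remains is an avoidable opening for selective loss, most visible in vital status, where a few unknowns per arm widen the possible range considerably.

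**What to change.** Leave every decision on treatment and procedures with the clinician, and add to section 5.6 text to this effect:

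> A decision taken on safety grounds ends only the treatment or procedure it concerns, and the reason is recorded. Unless consent is withdrawn, the patient stays in the trial for those already scheduled outcome, safety and vital-status assessments that the clinician judges safe. The GP call in section 5.1 applies to these patients. They are analysed in the arm to which they were randomised.

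Reconcile this with the rule in the same section that withdraws patients who need a glycoprotein IIb/IIIa inhibitor or do not receive study drug. Otherwise a patient whose study drug is not given for safety reasons could fall under both rules with opposite results. The 36-hour limit on adverse event recording need not change for this purpose.

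The cost is protocol wording and one case report form field for the reason. No visits are added. The downside is slight extra site effort to follow a few sicker patients.

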6. ASSESSMENT AND FOLLOW-UP

6.1 Subjects: A total of 100 subjects will be included in the study. Patient's demographic data will be collected.

6.2 Sampling and Dosing

6.2.1 Study subjects will have a $P2Y_{12}$ inhibitor administered (Ticagrelor or Cangrelor) after recorded verbal assent following randomisation. The time of loading dose will be recorded and the patient transferred to the cardiac catheterization suite. After the insertion of the radial or femoral sheath, 10 ml of whole blood will be drawn from this sheath at the first intracoronary balloon inflation time. A further 10 ml will be taken 4 hours post dosing (or as close as is practicable). Further sampling (15 ml) on the ward will take place 24-36 hours post dosing from an anticubital vein using a 21-gauge needle (see study summary tables). Samples taken will be analysed to assess $P2Y_{12}$ activity using VerifyNow TM (Accumetrics, San Diego, California, USA) and VASP Flow Cytometry tests. Peak Troponin levels will be assessed as well using the same blood samples.

6.2.2 Dosing: Patients will be divided into two arms; Oral Ticagrelor (50 patients) and Intravenous Cangrelor (50 patients) arms.

Ticagrelor arm: Patients will receive Ticagrelor 180mg loading dose on the cardiology ward prior to transfer to the catheter lab. Thereafter, a maintenance dose of 90mg twice daily will be given and continued for 12 months duration.

Cangrelor arm: Patients will receive Cangrelor administered at a rate of 30 micrograms/kg intravenous bolus followed immediately by 4 micrograms/kg/min intravenous infusion. The bolus and infusion will be initiated in the cardiac catheter lab prior to the PCI procedure and continued for at least two hours or for the duration of the procedure (to increase up to three hours), whichever is longer. 30 minutes prior to stopping Cangrelor infusion, Ticagrelor 180 mg will be given followed by 90mg twice daily maintenance dose continued for duration of 12 months. Cangrelor will be obtained directly from The Medicines Company, retained at the

pharmacy department at New Cross Hospital and issued by the pharmacy department for our clinical trial purposes only. Ticagrelor will be received by the pharmacy department and designated for our clinical trial purposes only.

Cangrelor vials and Ticagrelor tablets will be stored at controlled room temperatures (20°C to 25°C) in special cupboards on the cardiology ward. Only members of the research team will have access to the drug. Each vial contains Cangelor tetrasodium corresponding to 50 mg Cangrelor. After reconstitution 1 mL of concentrate contains 10 mg Cangrelor. After dilution 1 mL of solution contains 200 micrograms Cangrelor. Weight conversion charts in the catheter lab will be used to calculate the required dose of Cangrelor to be administered.

6.3 PHARMACODYNAMIC ANALYSIS

6.3.1 VerifyNow for P2Y12 Activity Analysis

VerifyNow [™] (Accumetrics, San Diego, California, USA) is a near patient test comprising a turbidimetric based optical detection system that measures platelet aggregation as an increase in light transmittance.

We are already using this system for clinical research in our department and it has regulatory approval for the assessment of $P2Y_{12}$ activity. VerifyNow has also been used in the assessment of Ticagrelor activity in a number of studies (16, 27, 28). 2 ml of whole blood is transferred into a Greiner Bio-One Vacuette containing 3.2% sodium citrate (Accumetrics, San Diego, California, USA) and inverted carefully, after which the tube is left at room temperature for a minimum of 15 and 30 minutes for $P2Y_{12}$ activity assay. The tube is then loaded into a specific assay device and analysed (within 4 hours from blood sampling) as per the manufacturers' instructions (Accumetrics). The system is calibrated daily electronically and full quality control is performed with each batch of assay devices. This system uses a similar principle to formal platelet aggregometry.

Results are shown as P2Y₁₂ reaction units (PRU) for P2Y₁₂ assay

6.3.2 VASP Flow Cytometry

VASP, an intracellular actin regulatory protein, is a substrate of both cyclic adenosine monophosphate (cAMP)- and cyclic guanosine monophosphate (cGMP)-dependent protein kinases (29).

Dephosphorylation of VASP follows P2Y₁₂ stimulation. Conversely, inhibition of the P2Y₁₂ receptor by Clopidogrel and stimulation of prostaglandin E₁-activated adenylyl cyclase induce phosphorylation of VASP by cAMP-dependent protein kinases. Thus levels of VASP phosphorylation/dephosphorylation reflect P2Y₁₂ inhibition/activation. Despite using a commercially available assay (Biocytex, Asnieres, France), VASP flow cytometry is primarily a research-based assessment owing to the complexity of the procedure and the requirement for significant technical expertise. It is seen by some as a gold standard test for P2Y₁₂ inhibition. Whole blood transferred to tubes containing 3.2% sodium citrate is

incubated with PGE1 or PGE1 and ADP for 10 minutes then fixed with paraformaldehyde, then platelets are permeabilized with non – ionic detergent. The cells are than labelled with a monoclonal antibody against 239-phosphorylated VASP and then a secondary fluoroscein isothicyanate-conjurgated polyclonal antibody. Analysis will be performed on a Becton Dickinson (Plymouth, UK) FACS Calibur flow cytometer, and 10,000 platelets will be gated per assessment as per the manufacturer's instructions. Results are expressed as percentage platelet reactivity index (% PRI). Samples will be taken to clinical chemistry department at New Cross Hospital and stored in freezers at minus 80 degrees. Samples will then be transferred in sealed protective containers to Wolverhampton University where flow cytometric analysis is performed under the supervision of [name].

VASP Flow cytometric analysis measures activity at the $P2Y_{12}$ receptor very effectively and thereby indirectly the activity of $P2Y_{12}$ inhibitor and has been shown to be of value in a number of clinical trials including one carried out by our own research group (30) (31).

6.4 TIMI Flow Grade

In acute ST elevation myocardial infarction early reperfusion of the occluded coronary artery, limits the size of infarction, reduces the degree of left ventricular dysfunction, and improves survival (32). Assessment of the degree of reperfusion was achieved using the Thrombolysis in Myocardial Infarction (TIMI) flow grading system developed in the TIMI 1 trial (Grade 0—No perfusion; Grade 1—Penetration without perfusion; Grade 2—Partial perfusion; Grade 3—Complete perfusion) (33). A larger improved survival was observed in patients who achieved TIMI grade 3 flow (34, 35). There is a nearly linear correlation between higher rates of early TIMI grade 3 flow and improved survival (35).

In our study, we will assess the index of blood flow through the culprit coronary artery using TIMI Frame Count (TFC). The TFC is a simple, reproducible, objective, and quantitative index of coronary flow that allows standardization of TIMI flow grades and facilitates comparisons of angiographic end points between trials (36).

The number of cine-frames required for contrast to first reach standardized distal coronary landmarks in the infarct-related artery (the TIMI frame count) will be measured with a frame counter on the GE cine-viewer. The first frame to be used for TIMI frame counting will be the first frame in which dye fully enters the artery. The last frame is defined as the frame when dye first enters the distal landmark branch.

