3. STUDY OBJECTIVES

- 1) To determine the degree and time-course of platelet inhibition in patients admitted with STEMI treated with IV Cangrelor vs oral Ticagrelor.
- 2) To assess the impact of Cangrelor vs Ticagrelor on the index of myocardial microcirculatory resistance using IMR.
- 3) To investigate the impact of Cangrelor vs Ticagrelor on markers of PPCI success (TIMI flow grade assessment to evaluate coronary blood flow after PPCI).
- 4) To assess ST segment resolution post PPCI.
- 5) To investigate the impact of Cangrelor vs Ticagrelor on initial myocardial infarct size based on Peak Troponin.
- 6) To investigate the impact of Cangrelor vs Ticagrelor on final myocardial infarct size by CMR at three months post PPCI.

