4.1 STUDY OUTCOME MEASURES

a) Degree of platelet inhibition measured with VerifyNow TM rapid platelet function analyser and also VASP flow cytometry at infarct vessel open time (also known as balloon time), 4 and 24-36 hours post dosing.

b) Index of Microvascular Resistance (IMR) measurement using pressure wire studies immediately following the PPCI procedure.

c) Measurement of thrombolysis in myocardial infarction (TIMI) flow grade using TIMI Frame Count.

d) ST Segment Resolution by ECG at 90-120 minutes post PPCI.

e) Infarct size by Peak Troponin at 24-36 hours post PPCI.

f) Final infarct size by CMR at three months in both patient groups (total of 100 subjects).

This study is not powered for clinical outcomes; however clinical and safety data will be recorded.

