5.3 RANDOMISATION

Potential patients will be reviewed by a member of the research team before randomisation to confirm eligibility. Once the eligibility of the patient is confirmed by the trial coordinators and the verbal assent is gained, randomisation will be carried out prior to patient's transfer to the cardiac catheter suite. Randomisation will be performed via a secure online web-based service. There will be a single password which will give access for randomisation for the trial on fully encrypted password-protected computers at the heart and lung centre, New Cross Hospital. The system is accessed via a secure connection (SSL) over the internet. This connection encrypts data between the user's internet browser and the server. Online randomisation is achieved by the trial coordinator entering a patient identifier (text field will be unique), own email address and the randomisation system password. Randomisation is by random permuted blocks to oral Ticagrelor or IV Cangrelor in 1:1 ratio. An email notification is generated displaying the chosen treatment group or code and sent to the email address given by the user randomising and the administrator email address. The administrator email address is the one provided when the system is set up (usually a trial coordinator or central trial email address). There is only one password and only members of the research team can perform a randomisation.

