7. STATISTICS AND DATA ANALYSIS

All statistical analysis will be performed in collaboration with [name], Professor of biomedical statistics at University of Wolverhampton on fully encrypted password-protected computers at New Cross Hospital.

Continuous variables will be compared using parametric and non-parametric tests as appropriate. Dichotomous variables will be compared by Fishers exact test. Logistic regression analysis will be used to predict the significant independent predictors of poor outcome post angiography.

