Appendix 2: Study Summary Tables

	1	2	3	4	5	6	7	8
Timepoint reference	Prior to PPCI	First IC balloon inflation	End of PPCI (following the life-saving part)	90-120 minutes post PPCI	4 hours post dosing	24-36 hours post dosing (15 ml blood for VASP/VerifyNow and peak Troponin)	Discharge	Three months post PPCI
Eligibility	X							
Medical History	x							
Verbal Assent	x							
Randomisation	x							
Dispensation of treatment	Х							
Initiation of either oral Ticagrelor or IV Cangrelor therapy	X							
Written Informed consent			Х					
Demographic data collection	X							
10ml blood collection for VASP/ VerifyNow		×			X	X		
IMR			Х					
ECG				X				

10ml blood								
collection for						x		
Peak Troponin						^		
Level (routine)								
TIMI Flow			X					
Grade								
Vital Status assessment							X	Х
BARC definition for bleeding			x					
Target Vessel Failure			X					
CMR								Х
Concomitant Medications	X	X	X	X	x	X	X	Х
Adverse Events review	Х	X	X	X	X	X to stop at 36 hours		

Study Steps	Time
1-Quick initial assessment of patients suitable for enrollment in the trial	Upon arrival at the Heart and Lung centre, New Cross Hospital
2-Verbal assent	After the initial assessment
3-Randomisation to either one of the two trial treatment groups	After obtaining verbal assent
4-Initiation of either oral Ticagrelor or IV Cangrelor therapy	Based on randomisation result
5-Primary PCI procedure	Once the second antiplatelet therapy is initiated (Ticagrelor or Cangrelor)
6-Blood sampling for P2Y12 inhibition estimation (using VASP phosphorylation and VerifyNow tests)	A- At the time of first intracoronary balloon inflation (10 ml of blood from the femoral or radial sheath) B- 4 hours post dosing (10 ml of blood from an anticubital vein) C- 24-36 hours post dosing (15 ml in total. 10 ml for VASP/VerifyNow and 5 ml for peak Troponin level. One needle prick)
7-IMR measurement	Immediately following PPCI (same procedure setting)
8-Patient information sheet will be provided and written consent sought	After successful completion of PPCI
9-ECG recording to assess the degree of ST-segment resolution.	90-120 minutes post PPCI

10-Peak Troponin level assessment	24-36 hours post PPCI.
11-TIMI flow grade assessment	Post PPCI
12-Vital Status assessment	On discharge and at three months post PPCI
13-CMR estimation of final myocardial infarct size	At three months post PPCI

STUDY COSTS

CMR	100 scans @ reduced research rate £100	= £10,000

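### The frame count has no value when dye never reaches the distal landmark, and no analysis by culprit artery is planned

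*Combined protocol and SAP*

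**What the plan says.** Section 6.4 says the trial will measure "The number of cine-frames required for contrast to first reach standardized distal coronary landmarks in the infarct-related artery". Counting starts when dye fully enters the artery, and "The last frame is defined as the frame when dye first enters the distal landmark branch". The section calls the landmarks standardised but gives no correction between arteries. It also sets out the flow grades, including "Grade 0—No perfusion; Grade 1—Penetration without perfusion", and gives no value for a patient in whom the last frame never occurs.

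Elsewhere the outcome is named as a grade. Section 3, objective 3, has "TIMI flow grade assessment to evaluate coronary blood flow after PPCI"; Appendix 2 has "11-TIMI flow grade assessment"; Section 4.1(c) joins the two as "Measurement of thrombolysis in myocardial infarction (TIMI) flow grade using TIMI Frame Count". No rule converts a count into a grade.

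On allocation, Section 5.3 says "Randomisation is by random permuted blocks to oral Ticagrelor or IV Cangrelor in 1:1 ratio" and mentions no strata. On analysis, Section 7 says "Continuous variables will be compared using parametric and non-parametric tests as appropriate". It adds Fisher's exact test for dichotomous variables and a logistic model for predictors of poor outcome. It names no stratum, covariate or missing-value rule for the frame count. Section 7.1 says that no formal sample size calculation was done and that the results will inform power calculations for later studies.

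**The concern.** Two separate things can go wrong if the count is analysed as Section 6.4 defines it.

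First, the outcome is undefined for exactly the patients with the worst result. A comparison of available counts leaves them out, and if one arm has more of them, the difference between arms shrinks. The trial is open label (Section 4), so a rule chosen after the films are read could be chosen knowing treatment.

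Second, the counts pool patients whose culprit arteries differ. If counts run longer in one artery than in the others, that difference adds noise to the comparison, and a chance imbalance in culprit artery between arms goes uncorrected. The extra variance and any shrunken effect would also pass into the later power calculations that Section 7.1 has in mind.

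**Working it through.** The plan has no power, alpha, effect size or SD for this outcome, so there is no figure of its own to reproduce. The first step is a reading of the text; the rest illustrates size.

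**Inputs.** From the documents: 50 per arm (Section 4). Assumed: two-sided 5% test; log-normal counts with coefficient of variation 40%, so log SD = √ln(1 + 0.4²) = √0.1484 = 0.385; true effect 0.56 log SD, which is (1.960 + 0.842) × √(2/50), the difference that gives about 80% power with 50 per arm; share p of culprits in a longer-count artery 40–50%; ratio r of its count to the others' 1.0 to 1.7; rate of landmark failure 1–10%. Power comes from simulation (4,000 to 8,000 runs per case, Monte Carlo standard error 0.5–0.8 points), comparing the Wilcoxon test with the van Elteren test stratified by artery.

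**1. Is the count defined for everyone?** The last frame needs dye to enter the distal landmark branch. Grade 0 is no perfusion, and Grade 1 is penetration without perfusion. Where dye does not reach the branch, there is no last frame and so no count. Sections 6.4 and 7 supply no substitute.

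**2. Power lost by ignoring the artery.** Power in %, unstratified → stratified:

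| r | p = 0.40 | p = 0.45 | p = 0.50 |
|---|---|---|---|
| 1.0 | – | 76.3 → 75.2 | – |
| 1.2 | 74.0 → 75.0 | 75.4 → 76.9 | 73.7 → 75.9 |
| 1.4 | 69.7 → 75.8 | 68.8 → 75.8 | 70.3 → 76.6 |
| 1.7 | 60.8 → 76.5 | 58.3 → 76.1 | 59.7 → 76.6 |

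The loss is about 1–2, 6–7 and 16–18 points at r = 1.2, 1.4 and 1.7. With no artery difference, stratifying costs 1.1 points. Under the null every test rejects in 4.7–5.4% of runs.

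The variance ratio explains this. Pooled over within-artery log variance = 1 + p(1−p)(ln r)²/0.1484. At p = 0.45 it is 1.055, 1.189 and 1.470, so a later trial sized on the pooled SD would need 5%, 19% or 47% more patients than one using the within-artery SD.

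**3. Chance imbalance.** At p = 0.45 the SD of the arm difference in artery share is √(2 × 0.45 × 0.55/50) = 0.0995, about 10 points. Each 10 points moves the comparison by 0.10 × ln r/0.385 = 0.047, 0.087 or 0.138 SD at r = 1.2, 1.4 or 1.7.

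**4. Effect shrinkage when the worst-flow patients have no count.** Take N(0, 1) against N(−0.56, 1), both cut at the point c exceeded by a fraction f of the worse arm. The mean of those left is μ − φ(c−μ)/Φ(c−μ). For f = 1, 2, 5, 10% the better arm loses 0.2, 0.4, 1.4, 3.3%. The raw difference falls from 0.56 to 0.539, 0.524, 0.487, 0.441. The remaining SD is 0.979, 0.965, 0.930, 0.885, so the standardised effect is 0.551, 0.543, 0.524, 0.498, a shrinkage of 1.7, 3.1, 6.5, 11.1%.

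**5. Exclusion against worst tied rank.** Power in %, no artery difference, by failure rate (worse-arm rate in the first two rows):

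| Failures | 1% | 2% | 5% | 10% |
|---|---|---|---|---|
| Worst-flow patients: exclusion | 75.5 | 74.3 | 70.3 | 64.2 |
| Worst-flow patients: worst rank | 76.8 | 77.5 | 77.0 | 77.2 |
| Equal in both arms, unrelated to drug: exclusion | 76.8 | 77.1 | 74.7 | 72.6 |
| Equal in both arms, unrelated to drug: worst rank | 75.2 | 74.1 | 67.8 | 58.3 |

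When half the failures are flow-driven the two are about level: 74.6 against 74.6 at 2%, and 71.0 (exclusion) against 72.0 (worst rank) at 5%.

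**6. Both changes together at r = 1.4, failures 1/2/5%.** Flow-driven: 68.6/65.8/61.3% as planned (unstratified, exclusion) becomes 76.1/76.6/76.7%. Unrelated to drug: 69.6/67.3/66.5% becomes 74.4/72.3/66.7%. In the last case the worst rank cancels what stratification gains.

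**The case against.** The strongest objection is that the artery point rests on a premise the documents do not contain. They do not say that counts differ by artery, give no culprit mix, and describe the landmarks as standardised. That stands as to size: every ratio above is an assumption, and at 1.0 stratifying is a small loss. It does not remove the point. A standardised landmark fixes where counting stops within an artery, and nothing says it makes counts equal across arteries.

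A reader might infer that leaving out the artery biases the comparison, or that the plan decides to disregard it. Neither is supported. Randomisation makes artery differences a matter of chance, type I error stays near 5%, and the missing adjustment is a silence in a generic analysis paragraph.

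A reader might also infer that the plan excludes the worst-flow patients. It does not say so; it gives them no value. If the grade were analysed, Grade 0 or 1 would be a valid, worst value and the gap would not arise. The no-count problem therefore applies only if the count is the analysed variable.

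Finally, ranking every unreached landmark as worst can do harm. At 2%, 5% or 10% of failures unrelated to drug it loses about 3, 7 or 14 points. This objection holds against a blanket rule, because a run that is unreadable or cut short says nothing about flow. It is why the worst rank should be limited to flow failure seen on the film.

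**Conclusion.** The point holds, conditionally, and is minor. If the frame count is analysed, Section 6.4 leaves patients whose dye never reaches the landmark without a value. If they are the worst-flow patients, dropping them shrinks the standardised effect by about 2–11% at assumed worse-arm failure rates of 1–10%. No section plans stratification or adjustment for culprit artery. That costs about 1–2, 6–7 or 16–18 points of power at assumed count ratios of 1.2, 1.4 or 1.7, and nothing if arteries do not differ.

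These sizes rest on an assumed effect of 0.56 SD, a 40% coefficient of variation and 40–50% of culprits in the longer-count artery. The documents supply only the 50 per arm. Few landmark failures are expected after PPCI, though no rate is given, and this is one of six outcomes in a pilot with no named primary. The mix of grade and count wording should be cleared up, but it is missing detail and not evidence of a wrong method.

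**What to change.** 1. Compare frame counts between arms with a rank test stratified by culprit artery (van Elteren), with the artery grouping fixed before analysis. The artery is already identified for the count and for IMR (Section 6.6), so this changes analysis wording only. The cost is about 1 point of power if arteries do not differ.

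2. Where the film shows that dye does not reach the landmark because flow is absent or incomplete (Grade 0–1), assign the worst tied rank and report the number per arm. Repeat the comparison without these patients as a sensitivity analysis. Treat unreadable or truncated runs as missing. This adds one recorded field, with the reason, and one extra analysis. The cost is some power if these flow failures are unrelated to drug; the equal-failure rows in the working show the size, and the sensitivity analysis is kept for that reason.

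The rule cannot recover patients withdrawn under Section 5.6 for glycoprotein IIb/IIIa inhibitor use, whose data are not collected.

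Separately, one sentence should state whether the count or the grade is the analysed endpoint.
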